4.3 Pathologic response criteria

4.3.1 At the completion of cytoreductive surgery, one 1cm nodule will remain in the peritoneal cavity during the perfusion procedure.

One nodule of tumor removed before hyperthermic perfusion treatment will be preserved for comparison. Tumor nodules will be divided in three portions and preserved in paraffin, a frozen block and as snap frozen tissue. Slides will then be cut and then used for immunohistochemical analysis of apoptosis, proliferation and autophagy.

4.3.2 Snap frozen tissue will be used for RNA extraction and gene expression profiling for the purpose of categorizing patient tumors based on response to hyperthermic peritoneal perfusion treatment. The Illumina platform will be used. A comparison of 6 patient samples, pre and post treatment, for a total of 12 samples will be analyzed. We will create a log of response comparing pre and post treatment gene expression and identify gene signatures for pathologic vs. non pathologic responders. Paraffin embedded samples will be used for tissue microarray, comparing pre and post treatment, to validate gene expression data at the protein level using IHC. Upon completion of full analysis, the tissue samples will be destroyed.

4.3.3 This information will be critical in the future in that it will allow the treating physician to identify which DSRCT patients would best respond to hyperthermic peritoneal perfusion cisplatin treatment by genetic tumor characteristics. ([name], pathologist, is part of the sarcoma center under the direction of [name])

4.4 Re treatment criteria

4.4.1 If patients return with recurrent measurable disease and experienced a 6 month disease free interval since the last HIPEC, they will be offered a reperfusion when there is radiographic evidence of recurrent intra-abdominal disease and no new contraindications. Patients having a reperfusion will be treated with 50 mg/M of cisplatin. (This is based on renal insufficiency seen in 2 patients who underwent 2 perfusions at 100 mg/M)

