## 2.2 Exclusion criteria

- 2.2.1 Patients will be ineligible if they have any concomitant cardiopulmonary disease which would place them at unacceptable risk for a major surgical procedure
- 2.2.2 Patients will be ineligible if they have disease outside of the abdominal cavity which is uncontrolled
- 2.2.3 Patients will be ineligible if they have a baseline neurologic toxicity of Grade 3 or greater (because of the potential neurotoxicity associated with platinum)
- 2.2.4 Patients who have failed previous intraperitoneal platinum therapy will be ineligible (“Failed” is having disease recurrence  $\leq$  3 months.)
- 2.2.5 Patients with Retroperitoneal Liposarcoma will be ineligible

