- 3.1.4 HIPEC and Cisplatin- Thirty minutes before HIPEC is begun, body temperature is cooled to 35°C. During the procedure, the cooling blanket and ice packs at the patients head and legs will be adjusted as necessary to maintain core body temperature below 38.5°C (as measured by esophageal probe). The catheters are connected to a perfusion circuit. The perfusate passes from a reservoir through a roller pump, heat exchanger and then into the abdominal cavity. Efflux from a second catheter is then recirculated through the reservoir and pump. The perfusion flow rate will be maintained to distend the abdomen 5 ( $\pm$ 2) liters/minute, and a perfusate volume will be maintained which moderately distends the abdominal cavity. Before the instillation of Cisplatin, the peritoneal cavity is warmed to a target of 40°C ( $\pm$ 1°C) as estimated by the influx/efflux catheter or peritoneal probe and the anesthesiologist will hydrate the patient with isotonic solution. The perfusion is continued for 90 minutes after adding the cisplatin. Cisplatin at 100 mg/M (1mg/1mL concentration in syringes) is to be added to the perfusate. The total maximum dose will not exceed

130 mg. Constant physical manipulation of the abdomen is maintained for the entire 90 minutes to assure even distribution of the perfusate. Peritoneal temperature is measured every 10-15 minutes by up to eight probes placed either beneath the peritoneal surface or at the influx and efflux catheters. At the end of the perfusion, the abdomen is re-opened and the perfusate is again irrigated from the abdominal cavity. The bowel is then thoroughly re-inspected for any perforations incurred and bowel anastomosis are completed. Throughout the procedure urine output must be maintained at 1-2 cc/kg/hr. Post-operative hydration will include 1.5 x maintenance normal saline or lactating ringer and maintenance of urine output of at least 1cc/kg/hr and replacing urine output cc/cc every hour with normal saline, for the first 48 hours to prevent hypovolemia and renal failure.

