#### 6.1.4 Administration

Cisplatin-100 mg/M {up to 130 mg/M maximum dose} (in 500 mL) will be added to a stable perfusion system.

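### A patient perfused before enrolment falls under two rules: 2.2.4 with 3.1.4 and 6.1.4 (recurrence after more than 3 months, 100 mg/M²), or 4.4.1 (6-month interval, 50 mg/M²); no section says which applies

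*Combined protocol and SAP*

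**What the plan says.** Four sections of the combined protocol and SAP bear on a second perfusion.

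- **Entry, 2.2.4:** "Patients who have failed previous intraperitoneal platinum therapy will be ineligible". Failure is then defined: it "is having disease recurrence" at or before 3 months. Later recurrence is not excluded by this criterion. The wording covers any intraperitoneal platinum, so previous cisplatin HIPEC falls within it.
- **Study dose, 3.1.4:** cisplatin at 100 mg/M² ("1mg/1mL concentration in syringes) is to be added to the perfusate"), with a total maximum of 130 mg. Nothing is said about patients perfused before.
- **Pharmacy section, 6.1.4:** the same 100 mg/M² ("maximum dose} (in 500 mL) will be added to a stable perfusion system"). No 50 mg/M² dose is listed and there is no exception for an earlier perfusion.
- **Retreatment, 4.4.1:** a returning patient must have "experienced a 6 month disease free interval since the last HIPEC" and is then perfused at 50 mg/M². The reason for that dose is given in parentheses: "This is based on renal insufficiency seen in 2 patients who underwent 2 perfusions at 100 mg/M"².

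Two further entry criteria are relevant. Section 2.1.8 requires adequate renal function and 2.1.11 requires recovery from the toxicity of earlier treatment. Neither mentions an earlier perfusion.

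**The concern.** Take a patient who had cisplatin HIPEC before this protocol and recurred after more than 3 months. For this patient the study perfusion is a second perfusion. The entry and dosing sections lead to 100 mg/M². The retreatment section, if it applies, leads to a longer interval and 50 mg/M².

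The case is plausible. An exclusion written for earlier intraperitoneal platinum shows that such patients were expected, and it admits some of them. The Rationale reports 9 DSRCT patients already treated with HIPEC at this centre, and 4.4.1 itself records patients perfused twice at 100 mg/M².

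The first stake is safety. A second perfusion at 100 mg/M² is the exposure that 4.4.1 associates with renal insufficiency, in a trial open from age 1 year. The second stake is interpretation. Renal events of Grade 3 or greater attributable to HIPEC count towards the toxicity rate in 4.2.3, and time to progression (TTP) after HIPEC updates the posterior in 4.2.2. Neither section separates first from second perfusions, so a mixture would be read as the result of a first perfusion.

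**Working it through.** The plan gives no figure on this point to reproduce. The check is a comparison of texts plus one dose ratio.

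**Step 1: same patient, two routes.** Classify a previously perfused patient by time from the last HIPEC to recurrence.

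| Recurrence after last HIPEC | Entry route (2.2.4, 3.1.4, 6.1.4) | Retreatment route (4.4.1) |
|---|---|---|
| 3 months or less | excluded | interval not met |
| more than 3, less than 6 months | not excluded; 100 mg/M² | interval not met |
| 6 months or more | not excluded; 100 mg/M² | reperfusion at 50 mg/M² |

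The routes agree only in the first row. In the second they differ on whether the patient may be perfused; in the third they differ on the dose.

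**Step 2: is there a rule of precedence?** Section 4.4.1 refers to the last HIPEC and to patients having a reperfusion, without saying that the earlier perfusion must have been given on this protocol. Sections 3.1.4 and 6.1.4 do not refer to 4.4.1, and 2.2.4 does not refer to it either. Nothing settles the order.

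**Step 3: what the renal observation supports.** In 4.4.1 the parenthesis follows the dose sentence. It is the stated basis for 50 mg/M². No reason is given for the 6-month interval.

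**Step 4: size of the dose difference.** Inputs: 100 mg/M² and the 130 mg cap (3.1.4), and 50 mg/M² (4.4.1).

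- The cap is reached at 130 / 100 = 1.3 M².
- Up to 1.3 M²: ratio = (100 × BSA) / (50 × BSA) = 2.0. At 1.3 M² this is 130 mg against 65 mg.
- Above 1.3 M²: ratio = 130 / (50 × BSA). At an assumed 1.8 M² this is 130 / 90 = 1.44.

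Section 6.1.4 expresses the maximum as 130 mg/M² rather than 130 mg. A limit in that unit would not bind a dose of 100 mg/M², and the ratio would stay at 2.0 for every BSA. At 1.8 M² the ratio is therefore 1.44 or 2.0, depending on which wording of the cap holds. That difference in units is a separate inconsistency.

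**Step 5: number affected.** The documents do not say how many previously perfused patients might enroll. The figure of 9 earlier DSRCT patients says nothing about who would return or what dose each had received. The number could be zero.

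**The case against.** The strongest reply is that the sections apply at different stages. Section 2.2.4 concerns entry. Section 4.4.1 is headed as retreatment criteria and opens with patients who return, which reads naturally as patients already treated on this study. Alternatively, 4.4.1 is a specific rule that qualifies the general dose in 3.1.4. Either reading removes the formal clash.

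This stands in part. A reader might infer that the sections flatly contradict each other and that 3.1.4 orders 100 mg/M² for every enrolled patient; the text does not go that far, since 3.1.4 is simply silent on earlier perfusion. But the two harmonising readings give opposite answers for the same patient, and neither is written down. Under the first, the safety issue remains: the renal observation concerns two perfusions at 100 mg/M², and the entry route then permits that exposure.

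It is also fair to say that 2.1.8 and 2.1.11 offer some protection. They reduce the concern. They do not replace a rule on repeat perfusion, because they look at renal function and recovery before the second exposure.

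Finally, reperfusion of patients first treated on study hardly touches the efficacy analysis: under 4.2.1 follow-up ends at relapse, death or 6 months, so a later reperfusion does not add a new TTP. That is correct, and it confines the analysis issue to patients perfused before enrolment.

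**Conclusion.** The concern holds as an unresolved overlap with a safety consequence. For a patient perfused before enrolment, the interval threshold is more than 3 months or 6 months, and the dose is 100 or 50 mg/M², depending on which section is followed. The ratio is 2.0 up to 1.3 M² and 1.44 at an assumed 1.8 M² under the 130 mg cap. The conclusion rests on the wording alone and needs no assumption about how many such patients exist. It should be settled before any such patient is enrolled.

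Four stronger inferences are not supported:

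- **That renal insufficiency also justifies the 6-month interval.** It is given as the basis for the dose only.
- **That a known share of earlier HIPEC patients would enter through the gap.** Such a share would need a distribution of times to recurrence. The Background gives a 9-month disease-free interval without saying whether it is a mean or a median, and no documented number would translate a share into enrolments.
- **That second perfusions would raise the chance of toxicity stopping by a stated amount.** Section 4.4.1 gives neither a grade nor a denominator for the renal insufficiency, while 4.2.3 counts only Grade 3 or greater renal events. Supposing that two such patients both have events, and comparing the result with an unconditional stopping probability, would not be like for like.
- **That second perfusions should therefore leave the toxicity rate.** Section 4.2.3 monitors toxicity in all patients. Removing those thought to be at greater renal risk would weaken the stopping rule.

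**What to change.** The sponsor and investigator should reconcile 2.2.4, 3.1.4, 4.4.1 and 6.1.4. The amended text should state:

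- whether a patient perfused before enrolment may enter as a new patient;
- if so, which interval rule and which dose rule applies;
- whether 4.4.1 covers only patients first perfused on this protocol.

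The choice of interval and dose is theirs; this review takes no position on it.

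If such patients may enter, keep them in the 4.2.3 toxicity monitoring, record previous perfusion as a flag in the database, and report their toxicity and TTP separately in addition to the overall results.

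The cost is a few sentences of amendment and one database field.

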4.4.2 Patients who progress will be offered other treatment alternatives

- 4.5 On study evaluation
  - 4.5.1 Patients will undergo laboratory tests, imaging and physical exam as per on study criteria.
  - 4.5.2 During HIPEC patients will have continuous core temperature monitoring by the esophageal probe and bladder probe. Peritoneal temperature is measured every 10-15 minutes by up to eight probes placed either beneath the peritoneal surface or at the influx and efflux catheters. If the temperatures are increasing above 40°C ( $\pm 1$ ), the temperature of the perfusate will be reduced. If the temperature readings are too low, the emphasis of the manual agitation will be redirected to that area of the abdomen.
  - 4.5.3 Patients will be followed postoperatively with daily CBC, sodium, potassium, chloride, carbon dioxide, BUN, creatinine, AST, ALT, calcium, albumin, magnesium, phosphorous, total bilirubin, alkaline phosphatase, amylase for 5 +/-2 days and then twice weekly until discharge; and post-discharge at day 14 +/-3 days and day 30 +/- 3 days and at 3 and 6 month (+/- 2 weeks) follow-up (Appendix 1) Adverse events will be assessed on the same timetable.
  - 4.5.4 Patients will be monitored in the PICU no less than 48 hours. If necessary, adult patients will be admitted to ICU.
  - 4.5.5 Evaluation of measurable disease will be performed one month, 3 months and 6 months postoperatively (+/- 2 weeks) using CT or MRI and physical exam. (CT or MRI scan performed only at 3 and 6 months)
  - 4.5.6 Audiology evaluation will also be performed at one month evaluation.
- 4.6 Concurrent Therapies
  - 4.6.1 Patients will be allowed to proceed with any post-operative chemotherapy including allogeneic or autologous bone marrow transplantation. No concurrent medications will be given at the time of study drug administration since this is only a 90 minute period in the operating room. However, baseline medications and all medications through the 30 days follow up will be entered into PDMS/CORe.
- 4.7 Pharmacokinetics (Optional)
  - 4.7.1 Blood and peritoneal fluid samples (2.0 ml) will be collected in purple top tubes, centrifuged, and supernatant or plasma collected and stored at -20°C until analyzed.
  - 4.7.2 Blood and peritoneal fluid will be collected prior to the start of cisplatin-HIPEC and then at times 0, 30, 60 and 90

minutes. An additional blood sample will be collected 24 hours (+/- 8 hours) after the start of HIPEC.

- 4.7.3 Platinum levels in plasma and perfusate will be determined by the laboratory.
- 4.7.4 Pharmacokinetic profiles of cisplatin in plasma and perfusate will be determined and compared.

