## 4.2 Response Criteria and Statistical Considerations

4.2.1 This is a phase II study of continuous hyperthermia peritoneal perfusion (HIPEC) in patients with desmoplastic round cell tumor (DSRCT) and non-DSRCT patients. The primary objective is to assess the efficacy of this treatment, with a primary endpoint of time to relapse. The historical median time to relapse for DSRCT patients without HIPEC treatment was about 1.6 months. A maximum of 22 patients will be enrolled in MDACC at an estimated accrual rate of 1 patient every 2 months including a total of 5 non-DSRCT patients. Patients will be followed up until relapse, death or for 6 months after the treatment, whichever ever occur first. It would be encouraging if the median time to relapse could increase to 3.2 months with the HIPEC treatment. The toxicity and efficacy will be monitored during the study, and all the data will be used to update the prior distributions for toxicity and efficacy parameters. The study will be stopped for toxicity and futility based on the following stopping rules.

4.2.2 The primary endpoint TTP will be monitored using the method of Thall et al. (23). Denote median (TTP) =  $m_H$  for patients without HIPEC treatment and  $m_E$  for patients with HIPEC treatment. We assume that TTP is distributed exponentially with mean of  $m_H$  and  $m_E$ , respectively, in patients without and with HIPEC treatment. Under a Bayesian model, we will further assume that  $m_H$  has an inverse gamma (IG) prior with parameters (16.2, 24.3), with a mean of median TTP=1.6 months and variance = 0.18. We also assume that  $m_E$  follows IG prior (2.03, 1.64) with the same median TTP as  $m_H$  but with a much larger variance (100) to reflect much greater uncertainty about TTP in patients with HIPEC treatment. The TTP data will be monitored continuously, and the study will be terminated early if  $\Pr(m_H + d < m_E \mid \text{data}) < 0.05$ , where  $d = 1.6$  month. Specifically, the trial will be stopped early if, given the current data, there is less than 5% chance that the median TTP will improve by more than 1.6 month in patients treated with HIPEC, compared to those without HIPEC treatment. The operating characteristics of this decision rule are summarized in [Table 1](#).

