#### 4.8 Off Study Criteria

- 4.8.1 Progression of disease- Once patients demonstrate progression of disease at follow up MRI or CT or PET-CT scans at 3 or 6 months, other therapies may be offered (but are not considered part of this study). Disease progression is defined by radiographically visible nodules greater than 1.5 cm. However, patients would be followed until death even after the 6 month follow-up by notification by primary oncologist.
- 4.8.2 Voluntary withdrawal
- 4.8.3 Non-compliance with follow-up scheme
- 4.8.4 At the time of cytoreductive surgery if patients are found to have disease which cannot be debulked to a diameter <1 cm in aggregate will be taken off study and not given the perfusion treatment.

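### Progression is imaged only at 3 and 6 months but no dating rule is stated; if it is dated at the scan, the futility rule built around a 1.6-month benchmark hardly ever stops

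*Combined protocol and SAP*

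**What the plan says.** - **Event.** Section 4.8.1: "Disease progression is defined by radiographically visible nodules greater than 1.5 cm". The same item places detection at the follow-up scans: "Once patients demonstrate progression of disease at follow up MRI or CT or PET-CT scans at 3 or 6 months".
- **Schedule.** Section 4.5.5 plans disease evaluation at one, three and six months, each within two weeks either way, but adds "CT or MRI scan performed only at 3 and 6 months". Appendix 1 agrees, so the one-month evaluation is a physical exam.
- **Follow-up.** Section 4.2.1 names time to relapse as the primary endpoint and states: "Patients will be followed up until relapse, death or for 6 months after the treatment, whichever ever occur first".
- **Benchmark and target.** Section 4.2.1: "The historical median time to relapse for DSRCT patients without HIPEC treatment was about 1.6 months", and "It would be encouraging if the median time to relapse could increase to 3.2 months with the HIPEC treatment".
- **Futility rule.** Section 4.2.2: "The TTP data will be monitored continuously". The trial stops if Pr(m_H + 1.6 < m_E | data) < 0.05, with inverse gamma priors IG(16.2, 24.3) for m_H and IG(2.03, 1.64) for m_E. The two m's are introduced as medians, and then the text reads "We assume that TTP is distributed exponentially with mean of" those same symbols.
- **Performance.** Table 1 gives a stopping probability of 0.775 at a true median of 1.6 months.
- **Final analysis.** Section 4.2.4 plans a median time to progression with a 95% confidence interval, Kaplan-Meier, log-rank and Cox.

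No section says how a progression first seen at a scan is dated, how interval censoring enters the likelihood, how patients not yet scanned contribute, or whether an exam finding, an off-schedule scan or a death is a progression event. How the historical 1.6 months was dated is not stated either.

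**The concern.** The first scheduled scan comes after the benchmark median. A scan-dated time is therefore about 3 months (about 2.5 at the early edge of the window) however soon the patient progressed. An exponential model that takes 3 months as an exact time sees a result close to the 3.2-month target.

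This is the trial's only futility rule, in a study that enrols children for major surgery with intraoperative chemotherapy. If it cannot respond to early progression, the protection that Table 1 reports is not there. The final Kaplan-Meier median has a related problem, because scan-dated events can occur only near 3 or 6 months.

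**Working it through.** **Inputs.** Priors, d = 1.6 and the 0.05 cut from 4.2.2; accrual of one patient per 2 months and 6-month follow-up from 4.2.1; scans at 3 and 6 months from 4.5.5. Assumptions: exponential times, Poisson accrual, a look before each new enrolment, nominal scan dates, and time between scans counted as event-free exposure. N = 20 because Table 1's percentiles reach 20 (4.2.1 states a maximum of 22).

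**Formula.** After k progressions and total time T, the posterior is m_E ~ IG(2.03 + k, 1.64 + cT), with c = 1 if m is the mean and c = ln 2 = 0.693 if m is the median.

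**Table 1 first.** Exact times, mean scale, true medians 1.0/1.6/3.2/4: 0.990/0.733/0.241/0.177, against 0.998/0.775/0.178/0.126 in Table 1. This is close but not a reproduction. All four rows come within two points (0.995/0.765/0.187/0.121) only with m_H fixed at 1.6, at least 2 patients before stopping and no 6-month truncation, none of which the plan states. On the median scale, exact times give 1.000/0.960/0.419/0.289.

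**Dating convention, true median 1.6 months, N = 20.**

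| Dating | m = mean | m = median |
|---|---|---|
| Exact | 0.73 | 0.96 |
| Midpoint of scan interval | 0.34 | 0.85 |
| Date of the scan | 0.000 | 0.004 |

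At a true median of 1.0 month, scan dating gives 0.000 and 0.086, against 0.998 in Table 1.

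**Check without simulation.** The rule stops only if 1.64 + cT falls below a critical value, which is 2.60, 10.21, 21.26 and 45.12 after 1, 5, 10 and 20 progressions. With scan dating T is at least 3k.

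- Mean scale: 1.64 + 3k = 4.64, 16.64, 31.64, 61.64, always above the critical value. Even if every patient has progressed at 3.0 months, the posterior probability is 0.18 after 1 patient, 0.33 after 17 and 0.34 after 22. The prior value is 0.093, so a patient who has progressed by the first scan raises the probability of benefit. With every scan two weeks early (2.54 months) the lowest value is about 0.14, at 22 of 22.
- Median scale: 1.64 + 0.693 × 3k = 3.72, 12.04, 22.43, 43.23. The cut is first reached at 15 of 15 (0.048; 14 of 14 gives 0.051). With 16 of 17 progressing and one clear at 6 months the value is 0.097. If every scan is two weeks early, the cut is first reached at 6 of 6 (0.048) and the stopping probability at 1.6 months is about 0.10. Scan dates spread evenly over the window give 0.006.

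**If some events carry their own dates.** With an assumed 10%, 25% or 50% of progressions at their true date and the rest scan-dated, stopping at 1.6 months is 0.03, 0.09, 0.24 (mean) or 0.12, 0.32, 0.65 (median). If every progression in the first month were found and dated at the one-month exam, it would be about 0.20 (mean) or 0.65–0.69 (median).

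**Kaplan-Meier median, scan-dated.** With n = 22 − 5 = 17 DSRCT patients, the median reads 3 months when at least 9 have progressed by the first scan.

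- True median 1.6: 1 − 2^(−3/1.6) = 0.727 and P(Bin(17, 0.727) ≥ 9) = 0.978.
- True median 3.2: 1 − 2^(−3/3.2) = 0.478 and P(Bin(17, 0.478) ≥ 9) = 0.426.

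**The case against.** **Early events may count.** The one-month evaluation includes an exam, and 4.2.1 ends follow-up at relapse or death. If such events count at their own dates, stopping is partly restored, as shown above. This stands: the near-zero figures hold only if none of them counts. The plan does not say that they do, and the radiographic definition in 4.8.1 points the other way.

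**Two defects could be merged.** A reader might infer that the missing dating rule alone moves the stopping probability from 0 to 0.96. It does not. The 0.96 is an exact-date figure on the median scale. The step from 0.73 to 0.96 comes from the separate conflict in 4.2.2 over whether m is a mean or a median. The effect of dating must be read within one column of the table.

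**Table 1's settings are unknown.** This also stands: that it assumed exactly known times is an inference, and differences from 0.775 partly reflect unstated settings. The main result does not depend on them. With m_H fixed at 1.6 and at least 2 patients, and with 6-month follow-up, exact times give 0.752 and scan dating still gives 0.000.

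**The historical figure may also be scan-dated.** If the 1.6 months was dated on a similar schedule, some of the Kaplan-Meier bias is shared. The documents therefore do not support saying that the comparison must favour the treatment, only that it does unless the dating was similar.

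**The monitoring method is cited.** Section 4.2.2 cites a methods paper, but a citation does not say which event date and likelihood this trial adopts.

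**Conclusion.** The concern holds in a conditional form and must be fixed. If progression is dated at the scan that shows it, and no exam finding, off-schedule scan or death is an event, the futility rule is nearly inert. At a true median of 1.6 months it stops 0.000 of trials on the mean scale, where the cut cannot be reached on scheduled-scan data whatever the results. On the median scale it stops 0.004, or about 0.10 with every scan two weeks early. Within one scale, exact, midpoint and scan dating give 0.73, 0.34 and 0.00 (mean) or 0.96, 0.85 and 0.004 (median).

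It would go too far to say that the rule can never stop under any reading, or that Table 1 is miscalculated. What the documents support is that Table 1's figures cannot be relied on until the event, its date and the meaning of m are fixed. The median in 4.2.4 has the same weakness: scan-dated, it reads 3 months in about 98% of trials at a true 1.6 months (n = 17, exponential times, no earlier events).

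**What to change.** 1. Define the progression event once and make 4.2.1, 4.5.5 and 4.8.1 agree: whether an exam finding, an off-schedule scan or a death counts, and on what date.
2. State in 4.2.2 whether m is the mean, S(t) = exp(−t/m), or the median, S(t) = 2^(−t/m).
3. Use a likelihood that respects the scan intervals and do not treat scan dates as exact times. One option is S(L) − S(R) for progression first seen at scan R after last clear scan L (0 if none), S(last clear scan) if none is seen, the density only for events whose date is known exactly, and no contribution from patients not yet scanned.
4. Recalibrate the cut-off and set a minimum number of scanned patients. With the current priors and 0.05 cut, this likelihood can stop after one progression at the first scan (posterior 0.047 mean, 0.039 median) and stops 0.35 (mean) or 0.46 (median) of trials at the 3.2-month target with N = 17. Then rerun Table 1 under the actual scan schedule and the DSRCT sample size, including non-exponential times.
5. In 4.2.4 report 3- and 6-month progression-free proportions with exact intervals and an interval-censored median. State how the historical 1.6 months was dated, or that this is unknown.

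By way of illustration only: on the median scale, a cut of 0.03 with a first look after 5 patients have had a 3-month scan and N = 17 gives 0.996/0.835/0.167/0.074 at medians 1.0/1.6/3.2/4. It is sensitive to shape: Weibull shape 0.7 lowers stopping at 1.6 months to 0.54, and shape 2 raises it at 3.2 months to 0.31. Other calibrations may serve as well.

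**Cost.** SAP wording and one simulation rerun, with no extra scans or patients. Each patient gives less information than an exact date would, and the first look comes somewhat later. In the illustration, mean patients treated is 7 at a true median of 1.0 month (Table 1: 4) and about 10 at 1.6 months (Table 1: 9).
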